8.8.2 Device-related Assessment include both TEAE and device complaints

The total incidence of Device-related safety events will be summarized for each treatment group as well as overall and would include device-related TEAEs and events related to

device complaints or failures. For device-related TEAEs, two categories will be summarized for each treatment as well as overall: needle-related TEAEs such as pain, bruise, and bleeding; and other device-related TEAEs, such as hyperglycemia or hypoglycemia. For device-related patient's complaints, incidence will be listed and summarized for each treatment and overall. Observed values and change from baseline will also be presented.

All the above analyses will be performed on the safety set for treatment period and run-in period.

8.8.3 Hypoglycemia

Hypoglycemia is a state produced by a lower than normal level of glucose in the blood. Hypoglycemia is classified as severe, documented symptomatic, asymptomatic, probable symptomatic, relative, nocturnal hypoglycemia. Patients will be instructed to record all hypoglycemic events in the patient's diary from Visit 2 until the EOT visit. The hypoglycemic events will be reviewed by the investigator and transcribed into the eCRF by the investigator or designee after the diary has been collected.

The classification will be derived as follows:

- Severe: the patients entered in the eCRF: "severe (external assistance required to resolve event)"
- Documented Symptomatic Hypoglycemia: the patient entered in the eCRF: symptomatic and checked the "glucose value was less than or equal to 70 mg/dL".
- Asymptomatic Hypoglycemia: the patient entered in the eCRF: asymptomatic (symptoms of hypoglycemia not present) and checked the "glucose value was less than or equal to 70 mg/dL".
- Probable Symptomatic Hypoglycemia: the patient entered in the eCRF: symptomatic and checked the "glucose was not measured".
- Relative Hypoglycemia: the patient entered in the eCRF: symptomatic and checked the "glucose value was over 70 mg/dL".
- Nocturnal Hypoglycemia: the patient has any of the 5 types above and also checked the "Nocturnal" time of the event.

Hypoglycemia event rate per patient per 30 days calculated between two visits is defined as total number of episodes between two visits divided by the number of days between the visits, multiplied by 30 days. The baseline hypoglycemia period is defined from the run-in period until randomization day. This rate will also be calculated per patient for nocturnal hypoglycemia episodes.

Hypoglycemia event rate per patient per 30 days will be analyzed using the same MMRM model as for the primary efficacy parameter (without imputing any missing data).

For change from baseline of hypoglycemia rate, a graphical display at scheduled visits, of LSMean and 2-sided 95% CI will be generated from the MMRM model. Additionally, mean (+/- SD) for actual measurements by visit will also be presented.

In addition, nocturnal hypoglycemia rate and incidence will be analyzed in a same way as overall hypoglycemic episodes.

Listings of hypoglycemic episodes and severe hypoglycemic episodes will be presented by visit for each patient. If a sufficient number of severe hypoglycemic episodes are reported, then incidence summaries similar to the incidence of hypoglycemic episodes will be included.

8.8.4 Hypersensitivity and Immune mediated adverse events

Incidence of hypersensitivity and immune mediated adverse events will be presented for treatment groups as well as overall.

8.8.5 Immunogenicity assessments

For antibody continuous variables, the MMRM model will include the fixed, categorical effect of treatment group assignment, visit, treatment group-by-visit interaction and the other fixed effect terms investigator and baseline value as covariates. Contrasts of LS mean at each scheduled visit will be used to evaluate all pairwise treatment comparisons, and 95% confidence intervals for treatment differences in LS means will be computed for each visit. For categorical data analyses, Fisher's exact test or Chi-squared test will be used.

The following analyses will also be performed.

- Incidence of ADA by visit, incidence of positive cross-reactive ADA by ADA status and by visit, and incidence of NABs.
- Analysis of potential impact of TEAR status on efficacy and safety parameters such as HbA1c, glucose control FPG, insulin dose, hypoglycemic rate, and Incidence of any injection site allergic reactions and hypersensitivity.

To explore the potential ADA impact on the subjects' glucose control, scatter plots of maximum TEAR values with HbA1c, FPG and total daily insulin dose will be displayed by treatment. In addition, the following analyses will be performed:

- TEAR effect on Efficacy will be assessed using the following:
 - 1) HbA1c and total insulin dose values by TEAR status and treatment group.
 - 2) A summary of subjects who experience meet vTEAR criteria, an increase in A1c of at least 0.2% from baseline, and an increase in the total dose from baseline at a protocol scheduled visit (where immunogenicity, A1c and dose all measured). This summary will be provided by visit, by treatment group, and overall.
- TEAR effect on Safety will be assessed using the following:

- 1) Hypoglycemic rate by treatment group and TEAR status.
- 2) Incidence of injection site allergic reactions and incidence of hypersensitivity in TEAR positive subjects.
- 3) Incidence of positive NAb by TEAR status and treatment group.

All the above analyses will be performed on the safety set.

The NAb actual assay results will not be available at the time of database lock (EDC database lock) for the analysis. However, the treatment will remain blinded during the laboratory assay. These data will be sent later from assay lab and statistical analysis will be performed according to pre-specified method in this SAP.

8.9 Other Safety Analyses

8.9.1 Laboratory Data

Change from baseline of laboratory measurements will be analyzed using MMRM with model terms of investigator, treatment, visit, treatment-by-visit interaction as fixed effects, and baseline value as covariate. The descriptive statistics for actual measurement and change from baseline along with treatment comparison will be performed at scheduled visits.

The percentage of subjects in categories such as normal, abnormal/non-clinically significant and abnormal/clinically significant will be summarized by treatment.

The percentage of subjects who meet potentially clinically significant criteria will be summarized by treatment groups.

The criteria for the Potential Clinically Significant Lab is listed in Appendix 10.3.

The following safety laboratory tests will be performed at times defined in the study schedules in Table 1.

Table 4: Laboratory Safety Tests

Hematology	Chemistry	Urinalysis	Other
Hemoglobin	Urea and Creatinine	pH	Urine/Serum hCG
Hematocrit	Glucose	Glucose (qual)	HIV and HBsAg
RBC count	Calcium	Protein (qual)	and HCVAb
Platelet count	Sodium	Blood (qual)	
WBC count	Potassium	Ketones	HbA1c
Total neutrophils (Abs)	Chloride	Nitrites	
Eosinophils (Abs)	AST, ALT	Leukocyte esterase	
Monocytes (Abs)	Total Bilirubin	Microscopy/culture ^a	
Basophils (Abs)	Direct/Indirect bilirubin		
Lymphocytes (Abs)	Alkaline phosphatase		
	Uric acid		
	Albumin		
	Total protein		
	CRP		
	C-Peptide		
	Lipid Profile		

^a Only if urine dipstick is positive for blood, protein, nitrites or leukocyte esterase.

Hematology, chemistry, urinalysis and other (parameters in last column of Table 4) will be summarized for treatment groups as well as overall by visits and parameters in each category.

8.9.2 Vital signs

Change from baseline of vital sign measurements will be analyzed using MMRM with model terms of investigator, treatment, visit, treatment-by-interaction as fixed effects, and baseline value as covariate. The descriptive statistics including actual measurement and change from baseline along with treatment comparison will be performed at scheduled visits.

The percentage of subjects who meet potentially clinically significant criteria will be summarized by treatment groups.

8.9.3 Physical examinations

A full physical examination will be performed at Visit 1 (screening), Visit 6 (randomization) and Visit 15 (EOT or ET). Height and weight will be assessed at Visit 1. The percentage of subjects in categories such as normal, abnormal/non-clinically significant and abnormal/clinically significant will be summarized at scheduled visits. But clinically significant changes from the screening procedures results will be recorded as adverse events. Physical examinations will be summarized for the safety analysis set.

8.9.4 Electrocardiograms (ECG)

The percentage of subjects in categories such as normal, abnormal/non-clinically significant and abnormal/clinically significant will be summarized by treatment group at screening and EOT.

8.10 Interim analysis

No interim analysis is planned for this study.

10 APPENDICES – SAS EXAMPLE CODES

[figure not shown]
10.1 Multiple imputation

Multiple imputation will be applied to fill in missing values for ADA binary response and for ADA titer.

For binary ADA response, if baseline ADA value is missing, the missing baseline value will be imputed (6 imputations) based on binomial distribution using probability of no missing baseline values from the same treatment group. After imputations, for subjects with negative baseline ADA (Section 10.1.1) missing post-baseline binary response (positive or negative) will be imputed using logistic regression multiple imputation. For subjects who are ADA positive at baseline (Section 10.1.2), missing post-baseline ADA continuous titer values will be imputed with same treatment group non-missing subjects using continuous MI model.

The steps are summarised below:

Section 10.1.1 describes the methodology for imputation of binary response, while Section 10.1.2 covers the imputation of continuous ADA titer, and Section 10.1.3 puts them together.

10.1.1 Multiple imputation for binary ADA response if baseline ADA is negative.

For purposes of these specifications, let $RESP_x$ represent the binary value (0 or 1) at Visit x , where x takes the values 0 (for Baseline) or 8–15. The seed that will be used in the multiple imputation of ADA binary response will be 40872021.

Missing values will be obtained from logistic regression imputation on the observed values of binary response. A fully conditional specification (FCS) method will be used to impute values from a non-monotone missing data pattern.

There are 3 steps to this process:

1. Create a dataset with one record per subject, containing all values of $RESP$ for all weeks (Baseline and Weeks 2–24 on one record); that is, each record would contain variables for $RESP_0$ and $RESP_8$ – $RESP_{15}$. The subject-level $RETRIEVED$ variable described in Section 8.7.2.1 can also be generated at this time for subjects who discontinued treatment, based on whether values after treatment discontinuation

- were retrieved (set retrieved=1) or remain missing (set retrieved=0).
2. Fill in missing values to make a monotone missing data pattern, by drawing random TEAR values from the binomial distribution based on the TEAR frequencies for the given visit within treatment group.
 3. Run a pattern mixture model logistic regression to impute missing values to generate 30 imputed datasets. This will generate a single pooled dataset containing one observation per subject per imputation. All missing values will have been filled in for each subject.

Step 1.

The dataset for this imputation has to put the values for all weeks onto one record. That is, the dataset would have one record per subject, with 8 values for RESP0 and RESP8–RESP15. One way this can be accomplished is the following:

```
data analysis (keep=usubjid RESP0 RESP8-RESP14);
set indata;
by usubjid avisitn;
array R {9} RESP0 RESP8-RESP15;
retain RESP0 RESP8-RESP15;
if first.usubjid then do;
    resp0 = base;
    do visit = 8 to 15;
        R{visit} = .;
    end;
end;
do visit = 8 to 15;
    if avisit = visit then R{visit} = aval;
end;
if last.usubjid then output;
run;
```

STEP 2.

First a flag needs to be created to indicate which missing values need to be filled in. This is a visit-level variable for each subject. For explanatory purposes, this variable will be referred to as EMPTY_x for Visit x. For each visit where a subject has a missing value, use the logic below:

- If there is a non-missing value for any visit AFTER Visit x, then EMPTY_x=0;
- Else if there are no non-missing values for any of the remaining visits, then EMPTY_x=1;

Then all records with EMPTY_x=1 have to have their RESP_x value filled in with a randomly generated 0 or 1. One way this can be accomplished is the following:

```
/** step 2: Make missingness monotone */  
%global mylrate novrate;
```

```
%macro getrate(visnum);
```

```
    proc sort data=indata;  
        by trtgroup;  
    run;  
    ods exclude all;  
    proc freq data=indata;  
        by trtgroup;  
        table RESP&visnum;  
    ods output onewayfreqs=pct;  
    run;  
    ods exclude none;
```

```
    data binom;  
        set pct (where=(RESP&visnum=1));  
        probresp = percent/100;  
        if trtgroup="MYL-1601D" then call  
            symput("mylrate",probresp);  
        else if trtgroup="NOVOLOG" then call  
            symput("novrate",probresp);  
    run;
```

```
%mend getrate;
```

```
%macro fillin (visit);
```

```
    %getrate(&visit);
```

```
    data indata;  
        set indata;  
        if empty&visit=1 then do;  
            if trtgroup="MYL-1601D" then  
                RESP&visit=ranbin(86537043,1,&mylrate);  
            else if trtgroup="NOVOLOG" then  
                RESP&visit=ranbin(48010557,1,&novrate);
```

```
end;  
run;
```

```
%mend fillin;
```

```
%macro monotone;  
  %do vis=8 %to 13;  
    %fillin(&vis);  
  %end;  
%mend monotone;
```

```
%monotone;
```

STEP 3.

Since SAS will not accept a binary variable as an independent variable in a logistic imputation model, continuous versions of the binary RESP variables. Both the continuous and categorical variables will be used during the regression. In the code below, the logistic regression code is different If there are <6 retrieved dropouts per group versus ≥ 6 .

```
/***/ setup: create numeric versions of binary variables  
***/  
data indata;  
set indata;  
array resps {7} resp0 resp8-resp14;  
array respns {7} respn0 respn8-RESPN14;  
do i=1 to 7;  
  respns{i} = resps{i};  
end;  
run;
```

```
/** step 3: Perform logistic regression imputation */  
  
/** Code to use if >=6 retrieved subjects per arm */  
proc mi data=indata nimpute=30 seed=40872021  
out=outdata;  
class resp8-resp15;  
var resp0n resp8 resp8n resp9 resp9n resp10 resp10n  
resp11  
    resp11n resp12 resp12n resp13 resp13n resp14 resp14n  
resp15;  
monotone logistic (resp8= resp0n) ;  
monotone logistic (resp9= resp0n resp8n) ;  
monotone logistic (resp10= resp0n resp8n resp9n) ;  
monotone logistic (resp11= resp0n resp8n resp9n resp10n)  
;  
monotone logistic (resp12= resp0n resp8n resp9n resp10n  
resp11n) ;  
monotone logistic (resp13=  
    resp0n resp8n resp9n resp10n resp11n resp12n) ;  
monotone logistic (resp14=  
    resp0n resp8n resp9n resp10n resp11n resp12n resp13n)  
;  
monotone logistic (resp15=  
    resp0n resp8n resp9n resp10n resp11n resp12n resp13n  
resp14n) ;  
mnar model (resp8-resp15 / modelobs=(retrieved=1));  
run;
```

```
/** Code to use if <6 retrieved subjects per arm */
proc mi data=indata nimpute=30 seed=40872021
out=outdata;
by trtgroup;
class resp8-resp15;
var resp0n resp8 resp8n resp9 resp9n resp10 resp10n
resp11
    resp11n resp12 resp12n resp13 resp13n resp14 resp14n
resp15;
monotone logistic (resp8= resp0n) ;
monotone logistic (resp9= resp0n resp8n) ;
monotone logistic (resp10= resp0n resp8n resp9n) ;
monotone logistic (resp11= resp0n resp8n resp9n resp10n)
;
monotone logistic (resp12= resp0n resp8n resp9n resp10n
resp11n) ;
monotone logistic (resp13=
    resp0n resp8n resp9n resp10n resp11n resp12n) ;
monotone logistic (resp14=
    resp0n resp8n resp9n resp10n resp11n resp12n resp13n)
;
monotone logistic (resp15=
    resp0n resp8n resp9n resp10n resp11n resp12n resp13n
resp14n) ;
mnar model (resp8-resp15 / modelobs=ccmv(k=1));
run;
```

10.1.2 Multiple imputation for continuous ADA titer if baseline ADA positive.

For purposes of these specifications, let ADA_x represent the continuous value for ADA titer at Visit *x*, where *x* takes the values 0 (for Baseline) or 8–15. The seed that will be used in the multiple imputation of ADA titer will be 41671703.

There are 3 steps to this process:

1. Create a dataset with one record per subject, containing all values of ADA for all weeks (Baseline and Weeks 2–24 on one record); that is, each record would contain variables for ADA₀ and ADA₈–ADA₁₅. The subject-level RETRIEVED variable described in Section 8.7.2.1 can also be generated at this time for subjects who discontinued treatment, based on whether values after treatment discontinuation were retrieved (set retrieved=1) or remain missing (set retrieved=0).
2. Run 30 Markov Chain Monte Carlo (MCMC) imputations to make the missing

values in the dataset have a monotone missingness pattern. This will produce a dataset with an index variable `_imputation_` and otherwise the same variables as the input dataset. It will have one record per imputation per subject.

3. Run a pattern mixture model regression imputation on each imputed dataset from Step 2. This will generate a dataset with the same structure as the input dataset, but will have the missing values filled in.

Step 1.

The dataset for this imputation has to put the values for all weeks onto one record. That is, the dataset would have one record per subject, with 8 values for ADA0 and ADA8-ADA15. One way this can be accomplished is the following:

```
data analysis (keep=usubjid trtp ADA0 ADA8-ADA15);
set indata;
by usubjid avisitn;
array y {9} ADA0 ADA8-ADA15;
retain ADA0 ADA8-ADA15;
if first.usubjid then do;
    ada0 = base;
    do visit = 8 to 15;
        y{visit} = .;
    end;
end;
do visit = 8 to 15;
    if avisit = visit then y{visit} = aval;
end;
if last.usubjid then output;
run;
```

Step 2.

```
/** step 2: Create monotone missingness using MCMC
imputation */
proc mi data=analysis seed=41671703 nimpute=1
out=outdata1;
mcmc impute=monotone;
var ada0 ada8-ada15;
run;
```

Step 3.

```
/***/ step 3: Perform PMM regression imputation ***/  
proc sort data=outdata1;  
run;  
  
/***/ Code to use if >=6 retrieved subjects per arm ***/  
proc mi data=outdata1 seed=41671703 nimpute=30  
out=outdata2;  
class retrieved;  
monotone reg(ada8-ada15 / details);  
mnar model (ada8-ada15 / modelobs=(retrieved=1));  
var ada0 ada8-ada15;  
run;  
  
/***/ Code to use if <6 retrieved subjects per arm ***/  
proc mi data=outdata1 seed=41671703 nimpute=30  
out=outdata2;  
by treatment;  
monotone reg(ada8-ada15 / details);  
mnar model (ada8-ada15 / modelobs=ccmv(k=1));  
var ada0 ada8-ada15;  
run;
```

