Study Week	-7 to -4	-4	-3	-2	-1	0	1	2	4	8	12	16	20	22	24	28
Study Days	-49 to -28	-28±3	-21±3	-14±3	-7±3	0±3	7±3	14±3	28±3	56±7	84±7	112±7	140±7	154±7	168±7	196±7
Sampling for immunogenicity ⁸	x					x		x	x	x	x	x	x		x	
Review diary, 7-point SMBG Profile and dose collection performed in the week before the visit ⁶				x		x		x	x	x	x	x	x		x	
Dose review of MYL-1601D, NovoLog [®] and Lantus [®] and dose adjust/instruction		x	x	x	x	x	x	x	x	x	x	x	x	x	x	
Dispense study medication and ancillary supplies		x				x			x	x	x	x	x			
Drug Accountability and Compliance				x		x		x	x	x	x	x	x		x	
Dispense subject diary		x		x		x		x	x	x	x	x	x			

1. Visits 3, 5, 7, 14 and 16 are telephone contacts/visits, in case required an actual site visit is possible (grey columns represent telephone contacts).
2. Standard-of-care specifics includes assessment and documentation of the following - Training on self-management of diabetes, lifestyle modification measures (includes maintenance of appropriate body weight, following recommended physical activity, avoidance of smoking and following the recommended diet); and monitoring to prevent complications.
3. Serum pregnancy test for women of childbearing potential will be done during screening and randomization visits (V1 and V6). During subsequent visits urine pregnancy test will be done, any positive urine test needs to be confirmed with serum test. At the randomization visit, both urine and serum pregnancy tests will be done; subject can be enrolled only if the urine pregnancy test is negative until serum result is provided.
4. A routine urine dipstick test will be performed by the site. A microscopic urinalysis will be performed by the central lab if the dipstick test result is abnormal and the Investigator deems it clinically significant and requests further evaluation.
5. Rescue criterion is evaluated on V12/Week 16 based on HbA1c measurement at V11/Week 12. Sites are required to receive the V11/Week 12 results prior to V12/Week 16 subject visit to enable Investigator to take decision on future steps.

6. The 7-point SMBG profile recorded via glucometer and recorded by the subject in the diary, measurement will be performed by the subject at home on 3 days (of which 2 days are consecutive) in the week before the visit.
7. Prior to randomization, Investigator is required to re-confirm subject eligibility to the study based on the data collected during the screening period, including the labs values recorded during screening.

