8. Immunogenicity samples: At Visits 1, 6, 8, 9, 10, 11, 12, 13 and 15. At each visit, five blood samples of 5 mL each (25 ml per visit) will be drawn for ADA and NAb.
9. V15 is regard as Early Termination from Treatment visit or Study End of Treatment visit. In case the subject discontinues treatment early, the site should explain the importance of data collection and make every effort to retain the subject, perform the remaining visits, off study treatment, per the SCHEDULE OF ACTIVITIES, up to the completion of Week 28/Follow-up call.
10. BMI is calculated at screening visit, randomization visit, week 12 and week 24.

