6.5.2.4 Immunogenicity Assessment

Blood samples (5 mL each) will be taken into serum separator tubes at each time point as outlined in [Table 3](#). At Visits 1, 6, 8, 9, 10, 11, 12, 13 and 15, five (5) blood samples of 5 mL each (25 mL total volume) will be drawn. The blood samples will be taken pre-dose by direct venipuncture, and the exact times of blood sampling will be recorded in the CRF. Two of the samples will be used to determine the presence of ADA against insulin aspart using the approach outlined below. One sample will be used to determine the presence of NAb against insulin aspart for samples that are ADA positive. Two samples will be collected and stored in reserve for potential supplemental immunogenicity testing and/or characterization including titer assessment if needed. Samples collected pre-dose at the randomization visit (Visit 6) will be considered as baseline. Samples collected at screening and the supplemental samples collected at baseline may also be used for method development and validation. Sample handling, processing, and storage instructions will be detailed in a separate laboratory manual.

A conventional radioimmunoprecipitation assay (RIPA) will be employed for the assessment of ADA in clinical samples. In this assay, samples will undergo a pre-treatment step that includes acid dissociation to release any anti-insulin antibodies complexed with free drug, followed by charcoal adsorption of the free insulin analog. The treated samples will be incubated with a fixed amount of ^{125}I -MYL-1601D tracer under conditions specified for each tier:

Screening Assay (Tier 1):

- RIPA Assay buffer only

Confirmatory Assay (Tier 2):

- RIPA Assay buffer only
- RIPA Assay buffer with excess unlabelled MYL-1601D
- RIPA Assay buffer with excess unlabelled Human Insulin
- RIPA Assay buffer with excess unlabelled NovoLog

Titer assay (Tier 3)

- RIPA Assay buffer only (multiple serial dilutions of the sample)

Anti-drug antibody complex formation with the tracer is measured via gamma counter and expressed as a percentage of bound to total radioactivity (%B/T).

In keeping with the multi-tiered sample analysis recommendations for immunogenicity testing from published white papers ([Mire-Sluis AR et al, 2004](#); [Shankar G et al, 2008](#)), and

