8 STATISTICAL METHODS

8.1 General statistical conventions

All statistical procedures will be completed using SAS version 9.3 or higher.

Unless otherwise stated, all statistical testing will be two-sided and will be performed using a significance (alpha) level of 0.05. Two-sided 95 % confidence intervals (CI) will be provided when relevant. 4 digits after decimal point will be used for all p-values.

All quantitative endpoints will be summarized using an 8-number summary (n, mean, standard deviation, median, 25th quartile, 75th quartile, minimum and maximum values). Unless otherwise specified, minimum and maximum will be presented with same number of decimal places as reported/collected, one additional decimal place for mean, median, 25th quartile and 75th quartile, and two additional decimal places for standard deviation. All qualitative endpoints will be summarized by the number of subjects meeting the endpoint and the percentage of subjects out of the appropriate population. The denominator will be displayed when needed.

For retests, unscheduled visits and visit end of treatment, in general, for by-visit summaries, data recorded at the nominal visit will be presented. Unscheduled measurements will not be included in by-visit summaries but will contribute to the scheduled visit if scheduled visit value is missing or the Last Observation Carried Forward (LOCF) value in case primary sensitivity analysis. The same principle will be applied to the visit end of treatment data.

Early termination data will be entered under the Visit 14 (week 18), but for summary tables it will be mapped to the next available planned visit number after their last scheduled visit. For example, should a patient discontinue at Visit 9, the Early Termination visit will have their Fasting plasma glucose and their HbA1c assay taken. The fasting plasma glucose would then be summarized under Visit 10 and the HbA1c under Visit 11.

All subject data, including those derived, will be presented in individual subject data listings. Unless otherwise stated, unscheduled visit results will be included in date/time chronological order, within subject listings only. All listings will be sorted by investigational site, patient number, date/time and visit. The treatment group as well as patient's sex and age will be stated on each listing. Unless otherwise stated, data listings will be based on all subjects randomized.

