10.1.3 Combining the multiple imputation results to derive TEAR status

At this point there should be two sets of imputed data, each containing 30 records per subject, with all visits on the same record. These will need to be merged by subject and imputation. Then the TEAR values will be computed for each subject and analyzed. There are 3 steps:

1. Merge the imputed ADA binary response dataset with the imputed ADA titer dataset, by `usubjid avisitn _imputation_`. Then generate TEAR responder status based on the Week 24 (Visit 15) ADA values using the same algorithm as was used for the original data. This dataset will have one record per imputation per subject, but the TEAR values will be non-missing for all subject visits. Note that the variable TEAR may vary from imputation to imputation for the same subject. That is supposed to happen.
2. Run the primary efficacy analysis to create the 90% confidence interval using the Wald confidence limit method within each imputation. That will result in 30 confidence intervals, one for each imputation.
3. Combine the 30 confidence intervals to generate one summary confidence interval to be presented in the table.

Step 1.

Merge the imputed titer values by `usubjid avisitn _imputation_` to make a single dataset. Then create a new variable for TEAR status by following the ADaM specs for the definition of TEAR events, but using the new imputed ADA data. Again, the dataset will contain one record per imputation per subject, with a new response variable added to every record. For the purposes of the next steps below, this new response variable will be called TEAR.

- a. If the subject was ADA negative at baseline then do:
 - i. If any of RESP8–RESP15 is positive, then TEAR=1 for that imputation for that subject
 - ii. Else TEAR=0 for that imputation for that subject
- b. Else if subject was ADA positive at baseline then do:
 - i. If $ADA_x / ADA_0 \geq 4$ for any visit, where x is in 8–15, then TEAR = 1;
 - ii. else TEAR=0

Step 2.

Use code similar to what was used to analyze the primary efficacy endpoint, but run the code by `_imputation_`. For example,

```
/** step 2: Analyze the imputed datasets */  
proc freq data=imputed;  
by _imputation_;  
table trt*tear / alpha=0.10 riskdiff (cl= wald column=2)  
;  
output=outmi riskdiff;  
run;
```

Step 3.

Combine the 30 estimated statistics into one using PROC MIANALYZE.

```
proc mianalyze data=outmi;  
modeleffects _rdif1_ ;  
stderr e_rdif1;  

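### SAP 10.1 imputes an ADA result for Visit 14, where no sample is scheduled, and counts it in the any-visit TEAR rule

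*SAP*

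**What the plan says.** **Sampling schedule.** Protocol Table 1, footnote 8: "Immunogenicity samples: At Visits 1, 6, 8, 9, 10, 11, 12, 13 and 15". Protocol 6.5.2.4 gives the same list ("At Visits 1, 6, 8, 9, 10, 11, 12, 13 and 15, five (5) blood samples of 5 mL each"), as does the footnote to SAP Table 1. Visit 6 is baseline. Footnote 1 of the protocol table: "Visits 3, 5, 7, 14 and 16 are telephone contacts/visits, in case required an actual site visit is possible". No ADA sample is listed for Visit 14 (Week 22).

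**Imputation appendix.** SAP 10.1.1 says that the visit index of the binary ADA variable "takes the values 0 (for Baseline) or 8–15", and SAP 10.1.2 indexes titer in the same way. In the binary branch, Step 1 builds the record with "data analysis (keep=usubjid RESP0 RESP8-RESP14". Step 3 gives Visit 14 its own model ("monotone logistic (resp14") and then uses it as a predictor of Visit 15. The text adds that every missing value is filled once this is done. SAP 10.1.3 derives the endpoint for baseline-negative subjects as follows: "If any of RESP8–RESP15 is positive, then TEAR=1 for that imputation for that subject". For baseline-positive subjects it looks for a titer ratio of at least 4 at any visit from 8 to 15.

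**Who counts as missing.** SAP 7.2.1 reserves that status for subjects with no post-baseline ADA data, or with gaps that leave TEAR status undecided.

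**What could sit under Visit 14.** SAP 8.1: "Early termination data will be entered under the Visit 14 (week 18"). Remapping to the next planned visit is stated for summary tables. The SAP 8.1 visit table gives Visit 14 the day range 148 to 161.

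**The concern.** TEAR is an any-visit endpoint, so each further visit that enters the rule can turn a non-responder into a responder and can never do the reverse. A visit at which nobody is scheduled to give a sample would have to be imputed for almost every subject, including those with complete data. Their TEAR status is already known from real samples, yet it would come to depend on a random draw. The NovoLog TEAR rate also sets the equivalence margin, so a rise in the rate moves both the estimate and the yardstick. The 8 to 15 index stands in the specification text and in the endpoint rule, not only in sample code, so a programmer who follows the SAP would include Visit 14.

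**Working it through.** **1. Counts.** Scheduled values per subject: baseline plus Visits 8, 9, 10, 11, 12, 13 and 15, so 1 + 7 = 8.

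| Item in SAP 10.1 | Stated | Listed |
|---|---|---|
| Values per record (10.1.1 and 10.1.2, Step 1) | 8 | 9 (baseline and Visits 8 to 15) |
| Binary Step 1 KEEP list | – | 8 (Visit 14 in, Visit 15 out) |
| Binary Step 3 predictor array | 7 | 8 (baseline and Visits 8 to 14) |
| Binary Step 2 fill loop | – | Visits 8 to 13 |

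Without Visit 14 the record has 8 values and the predictors of Visit 15 are baseline and Visits 8 to 13, which is 7. Both stated counts then agree.

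**2. One subject followed through.** Take a subject who is ADA negative at baseline and at all seven scheduled samples. Under SAP 7.2.1 nothing is missing and the subject is TEAR negative. Under SAP 10.1.1 and 10.1.3 the Visit 14 variable is empty, is filled by imputation, and makes the subject TEAR positive in every imputation where the draw is 1. The two sections disagree about the same subject.

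**3. Would the printed code do this?** Not as it stands; this is read from the code and was not run in SAS. Arrays `R` and `y` have 9 elements but are subscripted by visit number up to 15. The 7-element array lists 8 variables. The binary KEEP list lacks RESP15, which Step 3 needs. Step 2 does not fill Visit 14, so a completer with a Visit 15 result has a non-monotone record going into a monotone model. If nobody had a Visit 14 value, there would be nothing to fit. Visit 14 can be imputed only after the code is repaired to the stated index and some values sit in that slot.

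**4. The plan's margins.** Inputs: 250 per arm, and the quantiles in the SAP 10.2 code, z(0.95) + z(0.90) = 1.645 + 1.282 = 2.926 before rounding. Margin = 2.926 × √(2p(1−p)/250). At p = 10% this gives 7.85 (Table 2: 7.9), and at p = 20% it gives 10.47 (Table 2: 10.5). All 12 margins in Table 2 reproduce.

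**5. Effect of an extra imputed visit.** Let q be the chance that an otherwise TEAR-negative subject is imputed positive at Visit 14. The documents give no q; 1% to 10% is assumed. New rate = p + (1−p)q. For example, 0.20 + 0.80 × 0.05 = 0.24.

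| p (margin) | q = 1% | q = 2% | q = 5% | q = 10% |
|---|---|---|---|---|
| 5% (5.70) | 5.95% (6.19) | 6.9% (6.63) | 9.75% (7.76) | 14.5% (9.22) |
| 10% (7.85) | 10.9% (8.16) | 11.8% (8.44) | 14.5% (9.22) | 19.0% (10.27) |
| 20% (10.47) | 20.8% (10.62) | 21.6% (10.77) | 24.0% (11.18) | 28.0% (11.75) |

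With the same q in both arms a true difference shrinks by the factor 1−q: at p = 20% and q = 10%, 10.47 × 0.9 = 9.4 points. With true rates equal at p but q differing by arm, the estimated difference shifts by (1−p) times the difference in q.

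**6. Effect on the decision.** Simulation with 250 per arm, 30 imputations, 20,000 runs and the same q in both arms. Chance of declaring equivalence when the true difference equals the margin:

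| p | q = 0 | q = 10% |
|---|---|---|
| 5% | 0.087 | 0.119 |
| 10% | 0.076 | 0.084 |
| 20% | 0.068 | 0.070 |
| 30% | 0.058 | 0.054 |

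The simulation error is about √(0.07 × 0.93/20,000) = 0.002. With truly equal arms the chance stays between 0.78 and 0.81 for every p and q tried.

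**The case against.** The strongest reply is that this is labelled example code and cannot run, so it cannot silently bias anything. The stated 8 values, the array size of 7 and the fill loop ending at Visit 13 all suggest that Visit 14 was never meant to be included. TEAR is to follow separate dataset specifications that are not part of these documents, and SAP 7.2.1 already protects subjects with complete data. Much of this stands. It does not settle the matter, because the 8 to 15 index and the any-visit rule are written as specification. The counts point one way and the text the other, and the choice would fall to whoever repairs the code after SAP approval.

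Three stronger readings are tempting and are not supported.

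- A reader might infer from the KEEP list that Week 24 results are lost from the primary analysis. As printed, binary Steps 2 and 3 read a different dataset, so that line feeds nothing. The ARRAY and RETAIN statements beside it include Visit 15, and so does the titer KEEP list.
- A reader might infer that the primary rate is biased for nearly every subject. That requires code repaired to the stated index, values in the Visit 14 slot, and SAP 7.2.1 being overridden.
- A reader might infer that equivalence becomes easier to declare. The margin widens only as rates rise below 50%; Table 2 falls from 13.1 at 50% to 12.8 at 60%. With equal q the decision barely changes at TEAR rates of 10% to 30%.

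The early-termination route is also uncertain. Visit 14 is Week 22, not Week 18, and the protocol treats Visit 15 as the early-termination visit. The range of days 148 to 161 mostly lies between the permitted windows for Visits 13 and 15, so it would mainly catch off-schedule samples. By the SAP 8.1 table's own count, however, day 161 is within the ±7 days of Week 24 yet falls in Visit 14's range. Nothing says how such ADA results are placed for the primary analysis.

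**Conclusion.** The point holds as an error in the rule that derives the primary endpoint. SAP 10.1 gives ADA variables to a visit with no scheduled sample, and its TEAR rule lets an imputed value there override seven real negatives, against SAP 7.2.1. The code cannot produce this as printed; the exposure comes from repairing it to the index that the text states.

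The direction on the TEAR rate is certain: it can only go up. The size is not known, because q is not in the documents and the figures above are illustrations. If q is equal in both arms, the effect on the equivalence decision is small except at low TEAR rates, such as 5%. If q differed by arm, the estimated difference would be biased directly, but nothing in the documents shows that it would.

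**What to change.** In SAP 10.1.1 to 10.1.3, replace the 8 to 15 index by Visits 8 to 13 and 15 throughout: the text, KEEP lists, arrays, VAR, MONOTONE and MNAR statements, and both branches of the TEAR rule. Keep RESP15 and the treatment variable in binary Step 1. Subscript the arrays by position instead of visit number, and make their sizes match: 8 values per record and 7 predictors of Visit 15.

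In SAP 8.1, correct the visit named for early-termination entry. State that a real ADA sample recorded under the Visit 14 slot, whether from early termination or from days 148 to 161, is mapped to a scheduled ADA visit for the primary analysis, and say what happens if that visit already has a sample. Repeat in SAP 10.1.3 that a subject whose TEAR status is settled by observed results is not imputed.

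The cost is text and code edits. No new data are needed, and the design and sample size do not change.
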